2.2.1 Rationale for Biomarker Assessment

The primary goal of the biomarker assessments for this study is to evaluate potential mechanisms of resistance to asciminib.

Exploratory endpoints involving biomarker assessments for patients treated with asciminib, in comparison to those treated with bosutinib, will focus on 1) the PK/PD relationship; 2) BCR-ABL1 gene mutations that could influence the outcome of treatment regimens; and 3) the underlying biology of CML.

In order to evaluate tumor kinetics on a molecular level and to explore the role of mutations with respect to response to treatment, exploratory endpoints include assessment of mutations in the BCR-ABL1 gene at Week 1 Day 1, upon confirmed loss of molecular response and/or at end of treatment. Mutational status will be characterized in peripheral blood.

2.3 Rationale for dose and regimen selection

The dose and regimen of asciminib selected for this study is 40 mg BID. This dose is supported by pharmacokinetic, efficacy and safety data available from the ongoing [CABL001X2101] study.

During escalating doses of asciminib 10 mg to 200 mg on a continuous BID schedule in study [CABL001X2101], the 40 mg BID dose was shown to be active and well tolerated in CML-CP patients.

With respect to efficacy, no clear evidence of dose-response relationship was observed across dose levels when considering Complete Cytogenetic Response (CCyR) or MMR. However, as described below, PK-PD population modeling using change from baseline of BCR-ABL1 mRNA levels as a PD endpoint suggest a higher probability of achieving ≥ 1 log reduction at 6 and 12 months with 40 mg BID versus 20 mg BID.

With respect to safety, although no MTD (maximum tolerated dose) has been formally characterized, there is an increased toxicity observed at doses ≥ 80 mg BID (pancreatitis occurred at the dose of 80 mg in two patients who had an intra-patient escalation to 80 mg from 40 mg, and in one patient at the dose of 150 mg BID). Generally there is a trend for higher rates of discontinuation due to AE, DLT (dose limiting toxicity) and grade 3/4 AE with increasing doses.

With respect to overall exposure, the dose of 40 mg BID is expected to result in concentrations consistently above IC₉₀ *in vitro* concentrations. The estimates from study [CABL001X2101] were found to be above the threshold trough concentration required for 90% inhibition of pSTAT5 derived from a preclinical PK-PD KCL-22 mouse xenograft model (free IC₉₀: 30 to 121 ng/mL, after correction for protein binding) and *in vitro* gIC₅₀ assessed in the KCL-22 cell line (1 ng/mL = 2.1 nM after correction for protein binding).

A preliminary population PK-PD model has been developed using data from the [CABL001X2101] study (cut-off 2 May 2016). The time course of molecular response (change in BCR-ABL1 ratio % IS levels from baseline) was described using a semi-physiological model accounting for cell maturation, disease progression and existing resistance. Simulations performed (with 100 patients) using asciminib population PK-PD model revealed that at a dose of 40 mg BID, ~41% (CI₉₅%; 31-51%) of chronic phase CML patients having failed ≥ 2 TKI or intolerant to TKIs are likely to exhibit a 1 log₁₀ reduction of (%) BCR-ABL1 mRNA transcript levels from baseline at 6 months, and 53% (CI₉₅%; 43-63%) at 12 months, and predicting higher probability of achieving BCR-ABL1 mRNA ≥ 1 log reduction at 6 and 12 months with 40 mg BID versus 20 mg BID.

Additional preliminary PK-efficacy and PK-safety analyses to assess the exposure-response relationship for asciminib were conducted ([Section 1.2.1.2](#)). The efficacy measure used was Molecular Response (MR) which is defined as a decline in BCR-ABL1 transcript levels in clinical blood samples of patients with Chronic Myeloid Leukemia (CML). MR was evaluated as both a continuous variable (BCR-ABL1 transcript levels) and categorical variable (whether or not adequate decline in BCR-ABL1 was achieved). The safety measures used were occurrence of Common Toxicity Criteria (CTC) grade 2, 3 or 4 laboratory values for lipase and amylase.

Reviewing the totality of the efficacy, safety, and pharmacokinetic data derived from the [\[CABL001X2101\]](#) study, the recommended dose for asciminib in this phase 3 study is 40 mg BID. Of note, the dose of asciminib single agent BID is further being evaluated in patients with the T315I mutation. At present the recommended dose of 40 mg BID is for patients without the T315I mutation. For this reason, patients with the T315I mutation are excluded from this study.

2.4 Rationale for choice of combination drugs

Not Applicable.

2.5 Rationale for choice of comparators drug bosutinib

The guidance provided by the NCCN and the ELN ([Baccarani et al 2013](#)), recommends bosutinib as a treatment in CML-CP patients who fail first-line or second-line treatment with imatinib or nilotinib or dasatinib. Consistent with these recommendations and clinical practice, bosutinib was selected to be an appropriate comparator in a study of 3rd line CML-CP patients after failure of at least 2 prior TKIs, and is the comparator that will be used in the present study.

It is to be noted that bosutinib has no activity against the T315I and V299L mutant form of BCR-ABL1. Patients who have the T315I or V299L mutations documented in their medical record will already be excluded from this study. Bosutinib is known to be active against E255K/V, F317L/V/I/C, F359V/C/I, T315A, and Y253H and therefore, these mutations are not considered in the exclusion criteria for the current study.

Ponatinib is not selected as the comparator in the present clinical trial, because the comparator in this study needs to be an approved agent administered at the approved dose. Currently, the ponatinib dose is being evaluated in a randomized trial as a post-approval commitment due to the occurrence of vascular risks at the current approved dose of ponatinib. The dose of ponatinib that will be approved and will be used in practice at the completion of the present study may not be the approved dose at the time of initiation of the present study.

2.6 Risks and benefits

Appropriate eligibility criteria, as well as specific dose modification and stopping rules in the event of expected toxicities, are included in this protocol. Recommended guidelines for prophylactic or supportive treatment for expected toxicities, including management of study-drug induced adverse events are provided in [Section 6.3](#). Patients who have failed 2 prior TKIs are at increased risk of progression to more advanced phases of CML such as CML-AP and CML-BC. Currently available therapeutic agents in this setting are non-curative and patients remain at risk of progressing after short duration of remissions ([Khoury 2012](#)).

An important potential risk for patients enrolling on the experimental arm of the study with asciminib will be that this agent may be ineffective. However, the evidence to date at the doses to be administered in a similar population of patients in the study [CABL001X2101] suggests that asciminib is an active agent. Further, the adverse event profile of asciminib is similar qualitatively to that observed with other TKIs targeting BCR-ABL1 (Section 1.2.1.2). The risk of asciminib not being effective has been mitigated in that patients will be observed closely for evidence of efficacy, based on assessment of hematologic, cytogenetic and molecular response data, which will permit rapid decision making as to discontinuation of therapy if necessary.

Other risks to subjects in this trial will be minimized by compliance with the eligibility criteria and study procedures, close clinical monitoring, and adherence to dose modification and interruption guidance provided in the protocol.

The currently available information suggests that there is equivalence between the two arms with respect to benefit / risk to enable inclusion of patients in this study.

There may be unforeseen risks with asciminib which could be serious. Refer to the latest [Asciminib Investigator's Brochure] for additional details.

3 Objectives and endpoints

Objectives and related endpoints are described in Table 3-1 below.

Table 3-1 Objectives and related endpoints

Objective	Endpoint	Analysis
Primary		
To compare the MMR rate at 24 weeks of asciminib versus bosutinib	Major Molecular Response (MMR) rate at 24 weeks	Refer to Section 10.4
Key secondary		
To compare additional parameters of the efficacy of asciminib versus bosutinib	MMR rate at 96 weeks	Refer to Section 10.5.1
Other secondary		
To compare additional parameters of the efficacy of asciminib versus bosutinib	
 ● Cytogenetic response rate (Complete, Partial, Major, Minor, Minimal, no response) at and by all scheduled data collection time points including 24, 48 and 96 weeks ● MMR rate at all scheduled data collection time points (except 24 and 96 weeks which are already covered by primary and key secondary endpoints) ● MMR rate by all scheduled data collection time points including 24, 48 and 96 weeks ● Time to MMR ● Duration of MMR ● Time to CCyR ● Duration of CCyR ● Time to treatment failure ● Progression free survival ● Overall survival 	Refer to Section 10.5.2
To compare the safety and tolerability profile of asciminib versus bosutinib	Type, frequency and severity of adverse events, changes in laboratory values that fall outside the pre-determined ranges and clinically notable ECG and other safety data (vital signs, physical examination)	
To characterize the PK of asciminib in the CML-CP population	Trough plasma concentrations, PK parameters in full PK group: C _{max} , T _{max} , AUC _{0-12h} , CL/F	
To assess the safety of asciminib when administered as treatment after bosutinib failure according to the 2013 ELN Guidelines	Type, frequency and severity of adverse events, changes in laboratory values that fall outside the pre-determined ranges and clinically notable ECG and other safety data (vital signs, physical examination)	Refer to Section 10.6

Objective	Endpoint	Analysis

Exploratory
 
To evaluate the influence of factors such as cytogenetic response at baseline, failure/intolerance to prior TKIs, line of therapy, gender, race and age on the effect of asciminib with respect to the primary efficacy endpoint
 
To explore the exposure-response relationships of asciminib; evaluate the effect of population covariates
 
To characterize mutations in the BCR-ABL1 gene at Week 1 Day 1, upon confirmed loss of molecular response and/or at end of treatment and examine their association with molecular and cytogenetic response for asciminib vs. bosutinib
	
Major Molecular Response (MMR) rate at 24 weeks
 
Exposure-safety and exposure-PD analyses
 
BCR-ABL1 gene mutations at Week 1 Day 1, upon confirmed loss of molecular response and/or at end of treatment as determined by Sanger Sequencing
	
Refer to Section 10.6

[REDACTED]
	
[REDACTED]
	

To assess clonal evolution during treatment with asciminib vs. bosutinib
	
Low level BCR-ABL1 mutation profiles assessed by mass spectrometry at Week 1 Day 1, upon confirmed loss of MMR and/or at EOT. Clonal evolution of several genes implicated in CML assessed by Next Generation Sequencing (NGS) methods
	

[REDACTED]
	
[REDACTED]
	

To compare the impact of treatment on patient reported outcomes (PRO) including CML-specific symptoms, patient quality of life, and impact on work productivity and activity impairment from baseline and EOT between treatment arms in all patients
	
Change in symptom burden and interference from baseline over time according to the MDASI-CML PRO instrument Change in patient's impression of CML symptoms according to Patient Global Impression of Change (PGIC) Change in health utility from baseline over time according to EQ-5D-5L Change in work productivity and activity impairment over time according to WPAI
	

To compare the impact of treatment on health care resource utilization between treatment arms in all patients
 
To assess the efficacy of asciminib when administered as treatment after bosutinib failure according to the 2013 ELN Guidelines
	
Health care resource burden over time
 
 • Cytogenetic response rate (Complete, Partial, Major, Minor, Minimal, no response) at and by all scheduled data collection time points • MMR rate at and by all scheduled data collection time points 	
Refer to Section 10.6

Objective	Endpoint	Analysis
	
• Time to MMR• Duration of MMR• Time to CCyR• Duration of CCyR• Time to treatment failure	

4 Study design

4.1 Description of study design

The study is a phase 3, multi-center, open-label randomized study of oral asciminib versus bosutinib in patients with Chronic Myelogenous Leukemia in chronic phase (CML-CP), previously treated with 2 or more tyrosine kinase inhibitors.

The trial is designed to compare the efficacy and safety of asciminib with that of bosutinib in the treatment of patients with CML-CP having previously been treated with a minimum of two prior ATP-binding site TKIs. Patients intolerant to the most recent TKI therapy must have BCR-ABL1 ratio $> 0.1\%$ IS at screening and patients failing their most recent TKI therapy must meet the definition of treatment failure as per the 2013 ELN guidelines ([Baccarani et al 2013](#)). No more than 66 patients (approximately 30% of the overall trial population) that are intolerant to their most recent TKI therapy with BCR-ABL1 $< 1\%$ will be recruited in order to ensure that the CML third line patient population is adequately represented.

The study will also investigate secondary endpoints for efficacy, safety and PK of single-agent asciminib compared to bosutinib. Tolerability, PK, PRO and exploratory biomarker activities will also be assessed. Safety and efficacy data for patients switching to asciminib will be collected and analyzed separately.

Patients meeting all of the inclusion and none of the exclusion criteria will be randomized into one of the 2 treatment arms, based on a 2:1 randomization between the asciminib arm and the bosutinib arm.

[figure not shown]
The randomization will be stratified to ensure the study population is balanced between the arms with respect to cytogenetic response status (See [Section 7.2.1.2](#)) at screening as follows:

- Major cytogenetic response (complete or partial)
- No major cytogenetic response (minor, minimal or none)

Patients will continue to receive the assigned study treatments (asciminib or bosutinib) until the end of study treatment period as defined in [Section 4.3](#). Patients who discontinue their study treatment at any time during the study will be followed up for survival and for progression to AP/BC for up to 5 years from the date the last randomized patient receives the first dose (irrespective of treatment switch for patients failing bosutinib).

Serial PK samples over 12 hours will be collected on Week 2 Day 1 from at least 20 CML-CP patients (full PK group) on the asciminib arm, in addition to trough PK samples. These patients will be identified sequentially at selected sites that are capable of serial PK sampling over 12 hours. In the remaining patients in the asciminib arm and in patients that have switched to asciminib, sparse post-dose PK samples on Week 1 Day 1 and trough PK samples will be collected (sparse PK group).

Figure 4-1 Schematic of Study Design

4.1.1 Study treatment switch from bosutinib to asciminib

Patients with documented treatment failure (as per the 2013 ELN guidelines; [Baccarani et al 2013](#)) while on bosutinib treatment will have the option to switch to asciminib treatment within 96 weeks after the last patient has been randomized on study. The patients who switch to asciminib will be able to receive asciminib up to end of study treatment period. At the end of the treatment period for patients who, in the opinion of the investigator still derive clinical benefit, asciminib treatment will be made available through alternative options including, but not limited to, an expanded access/compassionate use/managed access program or access to commercial supplies in applicable countries. Discontinuation of asciminib for patients who have switched over from bosutinib must follow the guidelines provided in [Section 7.1.6](#). Eligibility criteria for patients switching to asciminib are described in [Section 7.1](#).

4.2 Timing of interim analyses and design adaptations

Not applicable. There are no formal interim analyses or design adaptations planned for this study. See [Section 8.6](#) for documentation of safety DMC.

4.3 Definition of end of study

The patients are treated in the study up to end of study treatment period defined as up to 96 weeks after the last patient receives the first dose or up to 48 weeks after the last patient has switched to asciminib treatment whichever is longer unless patients have discontinued treatment earlier. The end of the study, concluding the survival follow-up, will occur 5 years from the date when the last patient enrolled into the study receives the first dose of the randomized treatment.

The primary analysis (cut-off date) is defined as the date when all randomized patients have been on study treatment for 24 weeks ([Section 10.4](#)) or discontinued earlier. Subsequent to this

analysis, the primary clinical study report (CSR) will be developed. Following the cut-off date for the primary CSR, the study will remain open. Patients who are ongoing at the time of the primary analysis will continue to receive the assigned study treatments (asciminib or bosutinib) during the study treatment period as defined above. The end of study treatment analysis will be conducted with a cut-off date 30 days after the end of study treatment period to ensure all available treatment data from all patients in the study is analyzed and summarized in a CSR.

After the end of the study treatment period the assigned study treatment will be made available to patients who in the opinion of the Investigators are still deriving clinical benefit. This may be outside of this study through alternative options including, but not limited to, an expanded access/compassionate use /managed access program or access to commercial supplies in applicable countries.

Patients will be followed for survival and progression for up to 5 years from the date the last randomized patient receives the first study dose (irrespective of treatment switch for patients failing bosutinib). Information on subsequent treatments will also be collected. An updated analysis of OS and PFS will be performed at the end of the follow-up period in the final study CSR.

4.4 Early study termination

The study can be terminated at any time for any reason by Novartis. Should this be necessary, the patient should be contacted as soon as possible and instructed to stop taking study medication. The end of treatment visit should be scheduled and the same assessments should be performed as described in [Section 7](#) for a discontinued or withdrawn patient. The investigator may be informed of additional procedures to be followed in order to ensure that adequate consideration is given to the protection of the patient's interests. The investigator will be responsible for informing IRBs and/or ECs of the early termination of the trial.

5 Population

5.1 Patient population

Two-hundred and twenty-two (222) patients with CML-CP who had prior treatment with two or more ATP binding site TKIs will be randomized in a 2:1 fashion to receive either asciminib or bosutinib. No patients with a medical history of the T315I or V299L mutation at study entry will be included in the trial. Previous medical records should be used to confirm the patient's mutational status/history.

The definition of CML-CP will be according to the European Leukemia Network (ELN) criteria ([Baccarani et al 2013](#)), and is outlined below in the inclusion criteria.

The investigator or designee must ensure that only patients who meet all the following inclusion and none of the exclusion criteria are offered treatment in the study.

5.2 Inclusion criteria

Patients eligible for inclusion in this study have to meet **all** of the following criteria:

1. Male or female patients with a diagnosis of CML-CP \geq 18 years of age

2. Patients must meet all of the following laboratory values at the screening visit:
 - < 15% blasts in peripheral blood and bone marrow
 - < 30% blasts plus promyelocytes in peripheral blood and bone marrow
 - < 20% basophils in the peripheral blood
 - $\geq 50 \times 10^9/L$ ($\geq 50,000/mm^3$) platelets
 - Transient prior therapy related thrombocytopenia ($< 50,000/mm^3$ for ≤ 30 days prior to screening) is acceptable
 - No evidence of extramedullary leukemic involvement, with the exception of hepatosplenomegaly
- 3a. BCR-ABL1 ratio $> 0.1\%$ IS according to central laboratory at the screening examination, for patients intolerant to the most recent TKI therapy
4. Prior treatment with a minimum of 2 prior ATP-binding site TKIs (i.e. imatinib, nilotinib, dasatinib, radotinib or ponatinib)
5. Failure (adapted from the 2013 ELN Guidelines; [Baccarani et al 2013](#)) or intolerance to the most recent TKI therapy at the time of screening
 - Failure is defined for CML-CP patients (CP at the time of initiation of last therapy) as follows. Patients must meet at least 1 of the following criteria.
 - Three months after the initiation of therapy: No CHR or $> 95\%$ Ph+ metaphases
 - Six months after the initiation of therapy: BCR-ABL1 ratio $> 10\%$ IS and/or $> 65\%$ Ph+ metaphases
 - Twelve months after initiation of therapy: BCR-ABL1 ratio $> 10\%$ IS and/or $> 35\%$ Ph+ metaphases
 - At any time after the initiation of therapy, loss of CHR, CCyR or PCyR
 - At any time after the initiation of therapy, the development of new BCR-ABL1 mutations which potentially cause resistance to current treatment
 - At any time after the initiation of therapy, confirmed loss of MMR in 2 consecutive tests, of which one must have a BCR-ABL1 ratio $\geq 1\%$ IS
 - At any time after the initiation of therapy, new clonal chromosome abnormalities in Ph+ cells: CCA/Ph+
 - Intolerance is defined as:
 - Non-hematologic intolerance: Patients with grade 3 or 4 toxicity while on therapy, or with persistent grade 2 toxicity, unresponsive to optimal management, including dose adjustments (unless dose reduction is not considered in the best interest of the patient if response is already suboptimal)
 - Hematologic intolerance: Patients with grade 3 or 4 toxicity (absolute neutrophil count [ANC] or platelets) while on therapy that is recurrent after dose reduction to the lowest doses recommended by manufacturer
6. Eastern Cooperative Oncology Group (ECOG) performance status (PS) of 0, 1, or 2
7. Adequate end organ function as defined by (as per central laboratory tests):
 - Total bilirubin $\leq 1.5 \times$ ULN except for patients with Gilbert's syndrome who may only be included if total bilirubin $\leq 3.0 \times$ ULN or direct bilirubin $\leq 1.5 \times$ ULN

- Aspartate transaminase (AST) $\leq 3.0 \times \text{ULN}$
 - Alanine transaminase (ALT) $\leq 3.0 \times \text{ULN}$
 - Serum lipase $\leq 1.5 \times \text{ULN}$. For serum lipase $> \text{ULN} - \leq 1.5 \times \text{ULN}$, value must be considered not clinically significant and not associated with risk factors for acute pancreatitis
 - Alkaline phosphatase $\leq 2.5 \times \text{ULN}$
 - Creatinine clearance $\geq 50 \text{ mL/min}$ as calculated using Cockcroft-Gault formula
8. Patients must avoid consumption of grapefruit, Seville oranges or products containing the juice of each during the entire study and preferably 7 days before the first dose of study medications, due to potential CYP3A4 interaction with the study medications. Orange juice is allowed.
9. Written informed consent obtained prior to any screening procedures.
- 10a. Patients must have the following electrolyte values (as per central laboratory tests) within normal limits or corrected to be within normal limits with supplements prior to first dose of study medication:
- Potassium (potassium increase of up to 6.0 mmol/L is acceptable at study entry if associated with creatinine clearance within normal limits)
 - Total calcium (corrected for serum albumin); (calcium increase of up to 12.5 mg/dl or 3.1 mmol/L is acceptable at study entry if associated with creatinine clearance within normal limits)
 - Magnesium, with the exception of magnesium increase $> \text{ULN} - 3.0 \text{ mg/dL}$; $> \text{ULN} - 1.23 \text{ mmol/L}$ associated with creatinine clearance (calculated using Cockcroft-Gault formula) within normal limits.
11. Evidence of typical BCR-ABL1 transcript [e14a2 and/or e13a2] at the time of screening which are amenable to standardized RQ-PCR quantification.

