10.8 Sample size calculation

To test the null hypothesis that the response rate is equal in the two groups, based on two-sided 5% level of significance and with 90% power, 222 patients will be needed in total (i.e. 148 patients in the ABL001 arm and 74 patients in the bosutinib arm based on 2:1 randomization allocation). This assumes that ABL001 leads to a 20% improvement in the MMR rate at 24 weeks over bosutinib from 15% to 35% which corresponds to an odds ratio of 3.05.

The assumed bosutinib MMR rate of 15% at 24 weeks is based on previous trials evaluating bosutinib therapy ([Khoury 2012](#), [Gambacorti-Passerini 2014](#), [García-Gutiérrez 2015](#)).

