Purpose and rationale	
Purpose:
 
The purpose of this pivotal study is to compare the efficacy of asciminib with that of bosutinib in the treatment of patients with CML-CP having previously been treated with a minimum of two prior ATP-binding site TKIs with BCR-ABL1 ratios $\geq 1\%$ IS at screening. Patients intolerant to the most recent TKI therapy must have BCR-ABL1 ratio $> 0.1\%$ IS at screening and patients failing their most recent TKI therapy must meet the definition of treatment failure as per the 2013 ELN guidelines (Baccarani et al 2013). No more than 66 patients (approximately 30% of the overall trial population) that are intolerant to their most recent TKI therapy with BCR-ABL1 $< 1\%$ will be recruited in order to ensure that the CML third line patient population is adequately represented.
 
Rationale:
 
There remains an unmet need for new compounds in patients with CML who have failed at least two prior TKIs. Current practice suggests that a second generation TKI will have been used for first line therapy for about one half of patients with CML, meaning that most patients who have failed at least two prior TKIs will have failed at least one if not two second generation TKIs (such as dasatinib and/or nilotinib). Potentially, such patients may also have failed bosutinib and/or ponatinib (Soverini 2014). Patients having failed at least two TKIs may have limited sensitivity to the remaining available agents and, thus, there exists a need for new safe and effective therapy. In addition, mutations will have developed in 21 to 33% of patients that prevent the use of specific TKIs, increasing the need for a better and alternative compound (Soverini 2014). Omacetaxine, a chemotherapeutic agent, is available for patients who have failed at least two prior TKIs under these conditions but only in the US and Canada. This agent is not available for most patients globally, where a bigger unmet medical need is present. Thus, there remains an unmet need for patients with CML who have failed at least two prior TKIs despite the existence of multiple agents.

Primary Objective and Key Secondary Objective	
Primary Objective: To compare the Major Molecular Response (MMR) rate at 24 weeks of asciminib versus bosutinib
 
Key Secondary Objective: To compare MMR rate at 96 weeks of asciminib versus bosutinib

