Modification of the inclusion criterion of BCR-ABL1 transcript threshold required at study entry from a BCR-ABL1 ratio $\geq 1\%$ IS to BCR-ABL1 ratio $> 0.1\%$ IS (i.e. not in MMR) for patients with intolerance to most recent TKI treatment. The threshold presented in this inclusion criteria affects only patients who are intolerant to prior treatment, since patients failing prior treatment must fulfill the criteria defined by ELN guidelines ([Baccarani et al 2013](#)). Although the number of treatment options is increasing, especially for patients with imatinib intolerance, alternatives for patients with resistance and/or intolerance to at least two previous TKIs are limited ([NCCN 2018](#), [ELN 2013](#)). The reason of reducing the BCR-ABL1 ratio is that in routine clinical practice, physicians do not wait to observe increased BCR-ABL1 levels to switch treatment in patients with intolerance, which may increase the risk of disease progression, especially in patients with only limited further treatment options. This is in line with current CML treatment guidelines where the switch to an alternative therapy in intolerant patients is not linked to a BCR-ABL1 threshold ([NCCN 2018](#), [Baccarani et al 2013](#) and [Hochhaus et al 2017](#)).

Therefore, the threshold of $\geq 1\%$ BCR-ABL1 in the current trial is reduced to BCR-ABL1 ratio $> 0.1\%$ IS for patients with intolerance to most recent TKI treatment. No more than 66 patients (approximately 30% of the overall trial population) that are intolerant to their most recent TKI therapy with BCR-ABL1 $< 1\%$ will be recruited in order to ensure that the CML third line patient population is adequately represented. As the primary endpoint is the rate of MMR at 24 weeks a baseline molecular response level $> 0.1\%$ BCR-ABL1 is needed.

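### Amendment 3 sets the BCR-ABL1 > 0.1% entry floor for intolerant patients only, so a failing patient already in MMR can meet Section 5.2

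*Combined protocol and SAP*

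**What the plan says.** The Amendment 1 version (Section 5.2, criterion 3) required a central-laboratory ratio of at least 1% IS at screening from every patient. Amendment 3 replaced this with criterion 3a, which reads "BCR-ABL1 ratio $> 0.1\%$ IS according to central laboratory at the screening examination, for patients intolerant to the most recent TKI therapy". The Amendment 3 protocol summary limits the floor in the same way.

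Patients who failed their last TKI are handled by criterion 5; Section 4.1 says that "patients failing their most recent TKI therapy must meet the definition of treatment failure as per the 2013 ELN guidelines". Meeting any one failure item is sufficient. One of them is "At any time after the initiation of therapy, the development of new BCR-ABL1 mutations which potentially cause resistance to current treatment".

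The Amendment 3 rationale explains that the new threshold concerns intolerant patients because failing patients must satisfy the ELN definition. It then states: "As the primary endpoint is the rate of MMR at 24 weeks a baseline molecular response level $> 0.1\%$ BCR-ABL1 is needed".

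The Purpose paragraph of the Amendment 3 summary still describes the population as patients "with BCR-ABL1 ratios $\geq 1\%$ IS at screening", and gives the new rule in its next sentence. Sections 2.1 and 4.1 no longer carry the 1% figure.

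The Data analysis paragraph of the same summary defines a Week-24 responder by a ratio of 0.1% or less at Week 24. It sets no condition on the baseline value.

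**The concern.** The primary endpoint is a threshold state at Week 24, so it measures achievement of MMR only if nobody is in that state at entry. The universal 1% floor guaranteed this. Criterion 3a preserves the guarantee for intolerant patients and relies on the ELN failure definition for the rest. That definition does not do the same job. Its transcript levels (above 10% at 6 or 12 months, at least 1% with loss of MMR) describe the course on the last TKI, not the central screening value, and the mutation item has no level at all.

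A patient who enters in MMR and stays there is a response in whichever arm he or she is assigned to. Both rates rise, the difference shrinks, and the reported rate no longer means what the rationale says it should. The Week-96 key secondary endpoint is derived in a similar way and would be diluted in the same direction. The cap of 66 patients does not limit this route, because it counts only intolerant patients below 1%.

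**Working it through.** **1. Is the route open on the text?**

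- Criterion 3a: floor for intolerant patients only.
- Criterion 5: one failure item is enough, and failure must be present at screening.
- Mutation item: no BCR-ABL1 level.
- Criterion 11: needs a typical, quantifiable transcript but sets no minimum.
- Section 4.1: everyone who meets the inclusion criteria and no exclusion criterion is randomised.

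A failing patient at or below 0.1% with a new resistance mutation therefore meets Section 5.2.

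**2. Reproduce the planned power.** Section 10.8 of the Amendment 1 version states "based on two-sided 5% level of significance and with 90% power, 222 patients will be needed in total", with "148 patients in the ABL001 arm and 74 patients in the bosutinib arm based on 2:1 randomization allocation" and assumed MMR rates of 15% and 35%. Amendment 3 keeps 222 (Section 5.1). With pooled variance under the null and no continuity correction:

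power = Φ{[(pT − pC) − 1.96·√(p̄(1 − p̄)(1/74 + 1/148))] / √(pC(1 − pC)/74 + pT(1 − pT)/148)}

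Here p̄ = (74 × 0.15 + 148 × 0.35)/222 = 0.2833. The null standard error is 0.0642 and the alternative one 0.0571. Then (0.200 − 1.96 × 0.0642)/0.0571 = 1.30 and power is 90.3%. The same method returns 74 + 148 = 222 for 90% power. The stated odds ratio also reproduces: (0.35/0.65)/(0.15/0.85) = 3.05.

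**3. How many patients could enter this way?** On 21-Nov-2018, before Amendment 3, 86 patients had been randomised under the 1% rule. At most 222 − 86 = 136 remained, and intolerant patients among them keep a floor.

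**4. Dilution.** Let a share f of both arms enter in MMR and be in MMR at Week 24 with probability r. Each arm's rate is (1 − f)p + f·r, and the difference is (1 − f) × 20 points. The documents give neither f nor r; both are assumptions.

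| Patients in MMR at entry | f | Bosutinib / asciminib rate (r = 1) | Difference (points) | Power, r = 1 | Power, r = 0.7 |
|---|---|---|---|---|---|
| 0 | 0 | 15.0% / 35.0% | 20.0 | 90.3% | 90.3% |
| 1 | 0.45% | 15.4% / 35.3% | 19.9 | 89.8% | 89.9% |
| 2 | 0.90% | 15.8% / 35.6% | 19.8 | 89.2% | 89.4% |
| 3 | 1.35% | 16.1% / 35.9% | 19.7 | 88.7% | 89.0% |
| about 7 (0.03 × 222 = 6.7) | 3% | 17.6% / 37.0% | 19.4 | 86.5% | 87.2% |

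One such responder adds 1/148 = 0.68 points to the asciminib rate or 1/74 = 1.35 points to the bosutinib rate.

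**The case against.** **The route is narrow.** A reader might infer that loss of CHR, CCyR or PCyR, or new clonal abnormalities in Ph+ cells, open it just as wide, since these items also carry no transcript level. The documents do not support that. Failure must hold at screening, and the protocol treats MMR as implying CCyR: marrow cytogenetics are dropped once MMR is reached (Amendment 2 rationale), and duration of CCyR can be censored at a PCR showing MMR (Section 10.5.2, Amendment 1 version). CCyR means 0% Ph+ metaphases, so an abnormality found in Ph+ cells at screening does not fit with MMR either. This stands: the mutation item is the main opening.

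**The numbers are small.** Shares of 5% or 10% are easy to compute and look serious: with r = 1, power would be 83.8% or 76.7%. They would need about 11 or 22 such patients, that is 8% or 16% of the 136 still to be enrolled. Nothing in the documents suggests that many. This also stands.

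**Full retention is the worst case.** Discontinuation before Week 24 counts as non-response (Section 10.4.3, Amendment 1 version), and these patients enter as failures. The r = 0.7 column shows that this changes little.

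**The text may be less conflicted than it looks.** One could read the summary, the rationale and Section 5.2 as three competing entry rules. They are not. The operative criteria agree; the 1% phrase is a remnant in a purpose statement, and the rationale shows intent. The cap of 66 is a deliberate limit on one subgroup, not an error.

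None of this supplies the missing floor for failing patients.

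**Conclusion.** The point holds as a gap in the entry criteria that should be fixed. The condition that the rationale says the endpoint needs is not imposed on patients who enter through failure. The likely cost is about half a point to 1.6 points of power for one to three patients, and about 4 points if the share reached 3%. This assumes the planned rates of 15% and 35% in everyone else, equal shares in both arms, and full retention of MMR.

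Two stronger conclusions do not follow. First, the gap does not favour asciminib. Patients in MMR at entry are randomised like the others, so the expected effect is dilution of the difference, without inflation of the type I error. Second, it is not certain that such a patient would be analysed as a responder. The text available for this review stops in Section 7.1.2 of the Amendment 3 version. The responder rule is taken from its summary, and the amendment log says Section 10.4.3 was revised. A baseline-MMR rule there would protect the analysis, though not the entry criteria. The Week-96 effect has the same direction but is not quantified here, because it needs a further assumption about retention to 96 weeks.

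**What to change.** - Reword criterion 3a, in Section 5.2 and in the protocol summary, so that every patient, failing or intolerant, must have BCR-ABL1 above 0.1% IS by central laboratory at screening.
- Add this condition to the IRT eligibility check.
- Reconcile the leftover 1% phrase in the summary's Purpose paragraph with the amended criterion.
- Keep any patient already randomised at or below 0.1% in the full analysis set, and pre-specify a sensitivity analysis of the primary endpoint that counts such patients as non-responders.

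The cost is one clause in the next amendment, one corrected sentence and one edit check. No new test is needed, because Section 7.1.2 already requires the screening RQ-PCR result before randomisation. The sample size stays at 222 with 90.3% power under the planned rates. The downside is a few extra screen failures.
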